6. **Statistical Modeling.** We have proposed using OLS regression as the benchmark statistical model we intend to use to estimate the program’s effect on the primary outcomes. OLS is robust in large samples to misspecification. OLS is also a conventional approach to modeling dichotomous and count outcomes in evaluation because it produces estimates that are more immediately and readily interpretable, and because it tends to produce results that are substantively identical to the models that technically fit the data better. We will conduct tests that test the validity of this assumption and if there is a substantive difference in point estimates of interest produced by OLS and logit (or variant of – e.g. Firth logit) or statistical count models (e.g. Poisson and negative binomial families), we will report results of the models that fit the distributional characteristics of the data better (based on diagnostics and log-likelihood statistics).
- g. **Additional planned analyses:** We intend to investigate the following exploratory research questions in addition to the primary research questions described above.

Antecedents of Behavior

- a. What are the short-term (10th grade follow-up) and long-term (11th grade follow-up) impacts of the offer to participate in *PGC* (treatment) relative to the offer to participate in class as usual (comparison) on the following antecedents of participants’ sexual behavior:
 - i. Intentions to practice safe-sex behaviors
 - ii. Motivation to comply
 - iii. Normative belief strength
 - iv. Self-regulatory efficacy
 - v. Growth mindset
 - vi. Grit
 - vii. Decision-making skills
 - viii. Educational aspirations and expectations
 - ix. Educational ambitions
 - x. Perceived connection with peers
 - xi. School engagement/attachment
 - xii. Social competence
 - xiii. Self-efficacy in peer interactions

Primary Outcomes Measured at Long-term Follow-up

- a. What are the long-term (11th grade follow-up) impacts of the offer to participate in *PGC* (treatment) relative to the offer to participate in class as usual (comparison) on the primary outcomes of interest:
 - i. Sexual initiation
 - ii. Number of times having sex
 - iii. Number of sexual partners

Other Sexual Behaviors and Sexual Health Outcomes

- a. What are the short-term (10th grade follow-up) and long-term (11th grade follow-up) impacts of the offer to participate in *PGC* (treatment) relative to the offer to participate in class as usual (comparison) on the following sexual behaviors:
 - i. Number of times having sex without a condom
 - ii. Number of times having sex without any protection (prescription birth control or condoms)
 - iii. Number of sexual partners in the past year
 - iv. Ever being pregnant?
 - v. Times being pregnant?

Effects of Mediators on Primary Outcomes of Interest

- a. What are the short-term (10th grade follow-up) and long-term (11th grade follow-up) impacts of the offer to participate in *PGC* (treatment) relative to the offer to participate in class as usual (comparison) on participants' reported sexual initiation considering the following potential mediators:
 - a. Intentions to practice safe-sex behaviors
 - b. Motivation to comply
 - c. Normative belief strength
 - d. Self-regulatory efficacy
 - e. Growth mindset
 - f. Grit
 - g. Decision-making skills
 - h. Educational aspirations and expectations
 - i. Educational ambitions
 - j. Perceived connection with peers
 - k. School engagement/attachment
 - l. Social competence
 - m. Self-efficacy in peer interactions
- b. What are the short-term (10th grade follow-up) and long-term (11th grade follow-up) impacts of the offer to participate in *PGC* (treatment) relative to the offer to participate in class as usual (comparison) on participants' reported times having sex considering the following potential mediators:
 - a. Intentions to practice safe-sex behaviors
 - b. Motivation to comply
 - c. Normative belief strength
 - d. Self-regulatory efficacy
 - e. Growth mindset
 - f. Grit
 - g. Decision-making skills
 - h. Educational aspirations and expectations
 - i. Educational ambitions
 - j. Perceived connection with peers
 - k. School engagement/attachment
 - l. Social competence

- m. Self-efficacy in peer interactions
- c. What are the short-term (10th grade follow-up) and long-term (11th grade follow-up) impacts of the offer to participate in *PGC* (treatment) relative to the offer to participate in class as usual (comparison) on participants' reported number of sexual partners considering the following potential mediators:
 - a. Intentions to practice safe-sex behaviors
 - b. Motivation to comply
 - c. Normative belief strength
 - d. Self-regulatory efficacy
 - e. Growth mindset
 - f. Grit
 - g. Decision-making skills
 - h. Educational aspirations and expectations
 - i. Educational ambitions
 - j. Perceived connection with peers
 - k. School engagement/attachment
 - l. Social competence
 - m. Self-efficacy in peer interactions

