at the beginning of tenth grade. We describe below the specific operationalization of these three outcome measures (see Table 1 in Appendix for additional detail).

Sexual initiation

Sexual initiation is constructed as a dichotomous variable – participants are either coded as having ever had sex or not having ever had sex. Data used to assess the impact of the treatment (*PGC*) on sexual initiation are obtained from the following item on the *Participant Questionnaire*, which is administered to both treatment and control groups at baseline and the beginning of tenth grade:

- *Have you ever had any type of sex (oral, vaginal, or anal)?*

Persons who select *Yes* to the question are coded as 1, indicating that they have had sex. Persons who select *No* to the question are considered to not have ever had sex and are coded as 0 .

PGC will be considered to have a positive impact on sexual initiation if, as compared to participants who are assigned to the control group, a smaller proportion of participants who are offered *PGC* report sexual initiation at the beginning of tenth grade and the difference between groups is statically significant.

Times having sex

Times having sex is constructed as a continuous variable – the number of times in the past three months a participant engages in any type of sex (vaginal, oral, or anal).⁵ Data used to assess the impact of the treatment (*PGC*) on frequency of sex are obtained from the following item on the *Participant Questionnaire*, which is administered to both the treatment and control groups at baseline and the beginning of tenth grade:

- *In the past three months, how many times have you had any type of sex?*

Persons who indicate that they have never had any particular type of sex (vaginal, oral, or anal) or have not had any type of sex in the past three months are coded as having sex zero times.⁶

PGC will be considered to have a positive impact on times having sex if, at the beginning of the tenth grade, participants assigned to *PGC* report having sex fewer times than participants assigned to the control condition and the difference between groups is statically significant.

Number of sexual partners

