Number of sexual partners is constructed as a continuous variable – the number of sexual partners the participant reports that they have had in the past three months. Data used to assess the impact of the treatment (*PGC*) on number of sexual partners are obtained from the following two items on the *Participant Questionnaire*, which is administered to both the treatment and control groups at baseline and the beginning of tenth grade:

- The first question asks: *During your life, with whom have you had sexual contact?*

⁵ We are interested in exploring the effect of *PGC* on reduction of STI risk. Since STIs can be transmitted through any type of sexual contact (i.e., vaginal, anal, or oral), our measure of times having sex is not limited to sexual intercourse but includes all self-reported sexual activity.

⁶ The *Participant Questionnaire* contains sexual behavior questions that use a three-month recall period. As research has consistently found that memory of behaviors/events decreases over time and accuracy of recall is negatively associated with length of recall period (Clarke et al. 2008; Schwarz and Oyserman 2001), we use items with three-month recall periods to construct our measures of sexual behaviors since these should elicit more accurate responses than a longer recall period (e.g., six-month).

- If respondents select *Females*, *Males*, or *Females and males* to the first question, they are then asked this second question: *How many sexual partners have you had in the past 3 months?*⁷

Persons who indicate that they have never had sexual contact or have not had any sexual partners in the past three months are coded as having zero sexual partners.

PGC will be considered to have a positive impact on number of sexual partners in the past three months if participants assigned to *PGC* report fewer sexual partners at the beginning of tenth grade than participants assigned to the control condition and the difference between groups is statically significant.

- b. **Analytic sample:** In New York and North Carolina, 18 high schools are participating in the study and have supported the consent/assent, eligibility assessment, and enrollment processes for incoming ninth grade students (as described in section 3a above).

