- ii. **Identify and flag invalid responses:** The second step in the data screening process is to inspect the data for instances in which responses are invalid because they are outside of a pre-determined range of plausible or acceptable values. Each questionnaire type (e.g., baseline, post-program) has a codebook, which is prepared by a PRG staff, that contains variable names, valid variable values or ranges of values, and when applicable value labels.¹² Referring to the codebook, a senior or lead research analyst performs diagnostics in Stata to ensure that responses to all analytic measures are valid (i.e., data are within ranges specified in the codebook). A data analyst inspects the data using two commands in Stata. First the analyst uses the command *sum variable_name*, which provides summary statistics (mean, minimum, maximum, standard deviation) for all numeric variables. The analyst checks that the minimum and maximum values are valid. If this command reveals there are values out of range, the analyst then inspects the data using the command, *tab variable_name, missing*, which provides a frequency table of all values (including missing values) so the analyst can identify and flag all values that are out of range as invalid and recode these values to missing (code as “.i”).

Data that are recoded to missing are treated according to our missing data approach. Briefly, our benchmark approach is to adjust missing baseline data and include in analysis; we exclude observations with missing outcome data from analysis.

- iii. **Identify and flag outliers:** The third step is to identify and flag severe outliers. Outliers (operationally defined below) are values that are extreme compared to other observations but are not plainly invalid. In the data cleaning process, we inspect outliers so that we can try to ascertain whether they are in fact true (or plausible) values or potentially a result of measurement error. The only variables for which we inspect outliers are those used in the construction of our outcome variables (times having vaginal sex, times having oral sex, times having anal sex, and number of sexual partners) because they have no upper limit (all other variables used in analysis are either categorical or have predicated upper and lower bounds). Our approach to identifying and flagging outliers is as follows.¹³

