- First, in Stata we use the *lv* (letter-value display) command to identify severe outliers. We define values as severe outliers according their relation to the interquartile range (IQR). Severe outliers are defined as values outside of the *outer fences* of the population distribution.
 - $IQR = Q_3(3^{rd} \text{ quartile or } 75^{th} \text{ percentile}) - Q_1(1^{st} \text{ quartile or } 25^{th} \text{ percentile})$

¹¹ See [Comparing and Evaluating Youth Substance Use Estimates from the NSDUH and Other Surveys](https://www.samhsa.gov/data/sites/default/files/NSDUH-M9-Youth-2012/NSDUH-M9-Youth-2012.pdf) retrieved December 7, 2018 from <https://www.samhsa.gov/data/sites/default/files/NSDUH-M9-Youth-2012/NSDUH-M9-Youth-2012.pdf>.

¹² Regardless as to whether data are nominal, ordinal, or continuous, all response options are coded in Stata as numeric values; values are labeled according to corresponding category names when data are nominal or ordinal. As an example, the variable gender is a nominal variable; however, it is treated as a dummy variable where females are coded as “1” and males are coded as “0”. The only acceptable values for this variable then are 0 and 1; any other values are out of range.

¹³ Rules for identifying outliers are informed by the following: Hamilton, Lawrence C. 2006. *Statistics with Stata: Updated for Version 9* and *NIST/SEMATECH e-Handbook of Statistical Methods*, <http://www.itl.nist.gov/div898/handbook/>.

- Upper outer fence: $Q3 + 3*IQ$
- Lower outer fence: $Q1 - 3*IQ$
- Second, we create an outlier indicator variable, where observations deemed severe outliers are coded as 1, all others are coded as 0.

Our benchmark analytic approach is to include data flagged as outliers in analysis, because we do not know for certain whether the values are true or invalid. However, we also run sensitivity analyses that exclude these data and report substantive differences in the results section of the report.

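### The 3 × IQR outlier fence has no rule for IQR = 0 or for skip-pattern zeros, so sensitivity analysis 4 can remove ordinary reports as well as extreme ones

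*Combined protocol and SAP*

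**What the plan says.** Section 4c.iii limits the outlier screen to four unbounded counts: "The only variables for which we inspect outliers are those used in the construction of our outcome variables", namely "times having vaginal sex, times having oral sex, times having anal sex, and number of sexual partners". The criterion is "We define values as severe outliers according their relation to the interquartile range (IQR". The limits are "Upper outer fence: $Q3 + 3*IQ" and "Lower outer fence: $Q1 - 3*IQ", where IQ is the interquartile range. Flagging is mechanical: "Second, we create an outlier indicator variable, where observations deemed severe outliers are coded as 1, all others are coded as 0". The benchmark analysis keeps flagged values. Section 4f.iv item 4 and Appendix A Table 3 exclude them in a sensitivity analysis, and substantive differences go in the results section of the report.

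Zeros are defined for the outcomes in section 4a. For times having sex, students who never had sex or "have not had any type of sex in the past three months are coded as having sex zero times". For partners, those who never had sexual contact or "have not had any sexual partners in the past three months are coded as having zero sexual partners". Under section 4c.iv, students without a given behaviour skip its detailed items. Section 4c.v flags outliers in step 1 and considers logical imputation in step 3. Table 1 forms times having sex as the sum of the vaginal, oral and anal items.

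The plan is silent on three things: whether zero coding comes before the fence is computed, what to do when IQR = 0, and what happens to the sum when one of its items is flagged.

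**The concern.** A quartile-based fence suits data with spread in the middle half. Short-recall counts of sexual behaviour in ninth and tenth graders may sit mostly on one value. The IQR is then 0, the fence shrinks to that value, and every other report counts as a severe outlier, a report of one partner or one occasion included.

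Sensitivity analysis 4 is the plan's direct check on whether a few extreme self-reports drive the OLS estimates for the two count outcomes. The count models in item 6 change the model but do not remove those values. If the fence collapses, analysis 4 selects on the outcome itself. A full collapse leaves a constant outcome and would be noticed. A partial collapse still runs and yields an estimate labelled as free of outliers from which ordinary reports have also gone.

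**Working it through.** The plan gives no fence value, item distribution or prevalence, so there is no figure of its own to reproduce. The inputs from the plan are the two fence formulas, the four items and the summing rule. All shares below are assumptions, as are the 1,300 values and 400 answers. The thresholds do not depend on the number of students.

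**1. When the fence collapses.** IQR = 0 when one value v holds both quartiles, that is, when under 25% of values lie below v and under 25% above it. Then Q1 − 3 × 0 = Q3 + 3 × 0 = v, and every value other than v is flagged.

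**2. If skip-pattern zeros enter.** Here v = 0 once zeros exceed 75%. Take 1,300 values.
- 74.9% zeros (974): Q1 = 0 and Q3 = 1, so the fences are 0 − 3 × 1 = −3 and 1 + 3 × 1 = 4. In general, with Q1 = 0, the upper fence is 4 × Q3.
- 75.1% zeros (976): Q1 = Q3 = 0, both fences are 0, and all 1,300 − 976 = 324 positive reports are flagged.

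Percentile quartiles and letter-value fourths agree.

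**3. If only answered items are screened.** Students with lifetime contact but no recent partner still answer 0. Take 400 partner answers, with every report of two or more set to 2.

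| Zeros | Two or more | Q1, Q3 | Fences | Flagged |
|---|---|---|---|---|
| 20% (80) | 16% (64) | 1, 1 | 1 and 1 | 80 + 64 = 144; the remaining 256 are all 1 |
| 26% (104) | 16% (64) | 0, 1 | −3 and 4 | none |
| 20% (80) | 26% (104) | 1, 2 | −2 and 5 | none |
| 78% (312) | 7% (28) | 0, 0 | 0 and 0 | 60 + 28 = 88, all positive reports |

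The partner fence therefore fails in two regions: v = 1 when zeros and reports of two or more are each under 25%, and v = 0 when zeros exceed 75% of answers. The times items are largely protected on this reading, because students who never had that type of sex drop out of the base and positive counts are likely to spread over several values. Collapse would still follow if more than 75% of those answering an item gave 0.

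**4. Partial collapse of the summed outcome, if zeros enter.** Let A be the percentage positive on items that keep a working fence, u the percentage positive on any collapsed item, and o their overlap. The share of active students with a report on a collapsed item is u / (A + u − o).
- Shares positive 40, 20 and 5 (two items collapse): from 20/60 = 33% to 25/40 = 63%.
- Shares positive 30, 28 and 5 (one item collapses): from 5/63 = 8% to 5/30 = 17%.

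These students leave the analysis only if one flagged item drops the student or voids the sum. If the item is left out of the sum, they stay but their reports on it are lost.

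**The case against.** The strongest reply is that the most damaging branch is the one the text leans against. The fence is set on questionnaire items, skipped items are blank, and flagging precedes logical imputation. That stands as the likelier reading, though no section states it, and it leaves mainly the partner item exposed.

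Second, section 4c.iii says outliers are inspected for plausibility, and an analyst who saw reports of one partner flagged would probably notice. This is a partial safeguard. No step lets inspection reverse a flag, and the tables promised in footnote 9 and in step 2 of section 4c.v cover missing, inconsistent, unreliable and invalid data but not outliers.

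Third, analysis 4 only triggers reporting of differences. It cannot replace the benchmark, whereas the alternative models in item 6 can. That stands and limits the severity.

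A reader might infer that analysis 4 would remove ordinary reports and leave extreme ones in. The arithmetic does not support this: on a collapsed item the extreme values are flagged too, so the defect is over-exclusion. A reader might also take the percentages in step 4 as a forecast. They need zeros coded first, assumed item shares, and a rule that one flagged item removes the student or the sum. The documents supply none of these.

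**Conclusion.** The rule as written can give a misleading sensitivity result under either reading of the fence's base, because it has no provision for IQR = 0. The thresholds are arithmetic: more than 75% zeros on an item or, for partners, zeros and reports of two or more each under 25% of the answers screened. Whether the trial's data fall there is an assumption, since the documents give no prevalence.

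The reach is narrow: sensitivity analysis 4 for times having sex and number of partners. It would be wrong to infer that the primary results are at risk. The benchmark keeps all flagged values, so its estimates, p-values and Benjamini-Hochberg decisions do not change. Severity is minor.

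**What to change.** Replace the two-sided fence with an upper cut-off only, computed on non-zero reports pooled over arms. For the three times items, use Q3 + 3 × IQR of the non-zero reports. This settles whether skip-pattern zeros count.

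For partners, or whenever the non-zero IQR is 0, use a plausible maximum above 1, fixed before outcomes are seen by arm. Restricting the base to non-zero reports is not enough for partners: if more than 75% of reporters give exactly 1, the IQR is again 0. A high percentile is less suitable, because on a small item it flags the maximum almost by construction. In a simulation with 65 lognormal positive reports and no contamination, a 99th-percentile cut-off flagged exactly one value in 96% of 2,000 replicates.

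State whether a flagged item drops the student, voids the sum or is left out of it, and report the number flagged by item and arm.

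The cost is a few sentences in the plan and a few lines of code. The downsides are that a partner cut-off must be chosen in advance and that some genuine high values will still be flagged. With assumed lognormal times (sigma 1, medians 2, 4 and 8), the non-zero cut-off was about 13, 26 and 50 and flagged 3.2–3.5% of positive reports.
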